8.2.1. Overall Summary of Treatment-emergent Adverse Events

An overall summary of treatment-emergent adverse events (TEAEs) will be provided which tabulates the number and percentage of subjects who experienced a TEAE, related TEAE, treatment-emergent SAE, or treatment-emergent related SAE; the number and percentage of subjects who discontinued treatment or withdrew from the study due to an AE; and the number and percentage of subjects who died. This table will also be presented by subgroup based upon contemporaneous entry compliance of $\geq 80\%$, as described in Section 6.5.5.3.

AEs that occurred during major surgical/rehabilitation periods will be included in the overall summary of AEs (in the surgery subgroup column) but not in any of the other AE summary tables.

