3.2.2. Surgery and Rehabilitation

If a subject requires emergent or elective surgery while participating in this study, he may be treated with the dose and regimen of rFVIII Fc deemed appropriate for the type of surgery. If a subject had a major surgery before the implementation of Protocol Amendment 2, only major surgeries that were not prescheduled were to be reported as SAEs. However, for subjects having a major surgery after the implementation of Protocol Amendment 2, all major surgeries were to be reported as SAEs.

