- 1 minute before the first prophylactic dose on or after the last date among the dates for discharge from the hospital, post-operative visit 1, post-operative visit 2, the end of rehabilitation.
- If all of the dates mentioned above are missing, then select the first prophylactic dose after the date/time for the end of surgery. If the surgery time was not recorded or recorded as 00:00, then select the surgery date and impute 23:59 for the time. If the end date of the surgery is missing, then select the start date of the surgery and impute 23:59 for the time.
- If there are no prophylaxis doses following the latter of the 6 dates mentioned above, then select the latter of the dates and impute 23:59 for the time if otherwise there is no time associated with the given date (e.g., the subject completed the surgical/rehabilitation period but received no further prophylactic doses).
- If the overall end of study is declared while the subject is still in the surgical/rehabilitation period, then select the date of the end of study and impute 23:59 for the time.

If the treatment regimen after the surgical/rehabilitation period is the episodic regimen, then the end of the surgical/rehabilitation period is

- Imputed as 23:59 on the last date among the dates for discharge from the hospital, post-operative visit 1, post-operative visit 2, and the end of rehabilitation
- If all of the dates mentioned above are missing, then select the date of the end of surgery and impute 23:59 for the time. If the end date of the surgery is missing, then select the start date of the surgery and impute 23:59 for the time.

Two exceptions are noted:

- If 2 (or more) major surgeries are performed without an intervening discharge from the hospital, then the first surgical/rehabilitation period will end 1 minute before the start of the next surgery and the second surgical/rehabilitation period will end as described above.
- If minor surgery is performed during postoperative care or rehabilitation then the surgical/rehabilitation period for the minor surgery will start and end on the day of the minor surgery, at 00:01 and 23:59, respectively, if times are not otherwise provided or recorded as 00:00. The surgical/rehabilitation period for the major surgery will include the minor surgery (ie, the surgical/rehabilitation period for the major surgery does not stop and restart around the minor surgery) and will end as otherwise defined.

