8. SAFETY ANALYSIS

Safety data will be summarized for subjects from the parent study or subjects from the parent studies combined along with the overall total. The analysis population for safety analyses is defined in Section 4.3.

Adverse events (AEs) will be summarized for subjects from each parent study and overall for all subjects in study 8HA01EXT, regardless of treatment arm for subjects from studies 997HA301, 997HA307, and 997HA309, age cohort for subjects from study 8HA02PED, and treatment regimen in study 8HA01EXT.

In addition, all data from study 8HA01EXT will be provided in data listings.

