8.2. Adverse Events

AEs will be classified using the Medical Dictionary for Regulatory Activities (MedDRA) system organ classes and preferred terms. MedDRA version 15.0 will be used throughout the study. All AEs will be listed.

In general, AEs will be analyzed based on *incidence*, defined as the proportion of subjects who had at least one occurrence of an event out of the number of subjects in the Safety Analysis Set.

All adverse event listings will include the onset and resolution study days relative to 8HA01EXT Study Day 1. AEs that are emergent during a major surgical/rehabilitation period, AEs that are emergent on the day of surgery and AEs that occur during the gap of greater than 7 or 4 days will be flagged. In addition, a separate listing will be provided for AEs that are emergent during a major surgical/rehabilitation period.

AEs occurring during a major surgical/rehabilitation period with an onset date on the day the surgical/rehabilitation period starts or on the day of the surgery will be included in the summaries of the study AEs but excluded from the summaries or listings of AEs occurring during a major surgical/rehabilitation period. Consideration is given to AEs with an onset date at the start of the surgical/rehabilitation period in the event the pre-surgical dose was administered the day before the surgery.

Events of overdose will not be included in the AE summary tables unless they are reported as adverse events.

The algorithm for the determination of AEs that are emergent during a major surgical/rehabilitation period, AEs with an onset date on the day of the surgical/rehabilitation period starts or on the day of the surgery, and AEs that are emergent during a treatment regimen period when an onset date is partially or completely missing is described below.

- If the onset date of an adverse event is present, then the date of onset will be compared with the start/stop dates of the major surgical/rehabilitation period and treatment regimen period to determine whether the adverse event is during a major surgical/rehabilitation

period, on the day of the surgical/rehabilitation period starts or on the day of the surgery, or during a treatment regimen period. If the onset of the adverse event is on the day of the treatment regimen change, then it will be attributed to the previous treatment regimen.

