8.2.2. Treatment-emergent Adverse Events

In general, an AE will be regarded as treatment-emergent if it was present prior to receiving the first injection of rFVIIIIFc in the parent study and subsequently worsened in severity, or was not present prior to receiving the first injection but subsequently appeared before the subject's last visit on study or the follow-up phone call, whichever came later (or the date of withdrawal/loss to follow-up).

All AEs that occurred on or after the 8HA01EXT Study Day 1 will be considered treatment-emergent in study 8HA01EXT, regardless of the gap between the parent study and study 8HA01EXT. AEs that were treatment-emergent in the parent studies and carried over to study 8HA01EXT without worsening in severity will be considered the same AEs and will not be counted again in study 8HA01EXT.

The incidence of TEAEs will be summarized by system organ class (SOC) and preferred term. Unless specified otherwise, SOCs and preferred terms within each SOC will be presented alphabetically. For the purpose of summarization, a subject is counted once in a SOC or preferred term if the subject reported one or more events in that SOC or preferred term. Unless specified otherwise, percentages will be based on the number of subjects in the Safety Analysis Set.

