Subjects from study 8HA02PED: Summary of annualized bleeding rate by location and type of bleeds

Subjects from study 8HA02PED: Summary of annualized bleeding rate by the presence of target joints at screening in parent study

Subjects from study 8HA02PED: Summary of annualized bleeding rate by ePD entry compliance
Summary of subject's assessment of response to rFVIII Fc injections for the treatment of bleeding episodes

Summary of number of injections required for resolution of a bleeding episode

Summary of dose (IU/kg) of rFVIII Fc for resolution of bleeds

Summary of results and change from study 8HA01EXT baseline: CHO-KLAT total score from the Child Self-report Questionnaire

Summary of results and change from study 8HA01EXT baseline: CHO-KLAT total score from the Parent/Proxy Questionnaire

Summary of results and change from study 8HA01EXT baseline: Hemo-Sat total score and subscores

Summary of EQ-5D-Y descriptive system

Summary of results and change from study 8HA01EXT baseline: EQ-5D-Y visual analogue scale

Summary of hemophilia-related health-economic parameters

Summary of health economic parameters for all physician and emergency room visits

Summary of results and changes from study 8HA01EXT: Hemophilia Joint Health Score (HJHS)

Overall groups of subjects in 8HA01EXT (as described in Section 5.1):

Summary of compliance for the treatment of bleeding episodes

Summary of prophylactic dose compliance

Summary of prophylactic dosing interval compliance

Summary of prophylactic compliance

Summary of EPD entry compliance

Overall summary of rFVIII Fc treatment-emergent adverse events

Summary of rFVIII Fc treatment-emergent adverse events by preferred term in descending order of incidence

Summary of rFVIII Fc treatment-emergent adverse events by relationship to treatment

Summary of rFVIII Fc treatment-emergent serious adverse events

Summary of anti-rFIIIV Fc antibodies

Surgery subgroup – Summary of Investigators'/Surgeons' assessment of subjects' hemostatic response to rFVIII Fc post major surgery

Surgery subgroup – Number of injections and dose required to maintain hemostasis during major surgery

Surgery subgroup - Estimated total blood loss during major surgery

Surgery subgroup – Total rFVIII Fc consumption (IU/kg) per major surgery

Surgery subgroup - summary of number of bleeds after surgery per major surgery

Summary of Investigators'/Surgeons' assessment of subjects' hemostatic response to rFVIII Fc post minor surgery

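### Adverse events starting after the day of major surgery, within the surgical/rehabilitation period, are left out of every AE table except one overview column

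*SAP*

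**What the plan says.** **Exclusion.** SAP 8.2.1 places adverse events (AEs) from major surgical/rehabilitation periods in the overall summary of treatment-emergent AEs "in the surgery subgroup column) but not in any of the other AE summary tables".

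**What is put back.** Under SAP 8.2, events starting on the first day of the period or on the day of surgery "will be included in the summaries of the study AEs but excluded from the summaries or listings" for surgical periods.

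**Length of the period.** For subjects on prophylaxis, SAP 5.3.3 ends it "1 minute before the first prophylactic dose on or after the last date among the dates for discharge from the hospital", the post-operative visits and the end of rehabilitation. For subjects on the episodic regimen it ends at 23:59 on the last of those dates.

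**Denominator.** SAP 8.2 defines incidence as subjects with at least one event "out of the number of subjects in the Safety Analysis Set". SAP 8.2.2 repeats that, unless stated otherwise, "percentages will be based on the number of subjects in the Safety Analysis Set".

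**Who is summarised.** SAP 8 says AEs "will be summarized for subjects from each parent study and overall for all subjects in study 8HA01EXT". It mentions no surgery column.

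**Surgery as a serious event.** Before Protocol Amendment 2, "only major surgeries that were not prescheduled were to be reported as SAEs"; after it, every major surgery is (SAP 3.2.2; Protocol 15.1.3).

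**Protocol.** Section 16.6.2 plans AE incidence overall, by severity and by relationship, and removes no surgical time. Section 16.4.2 sets surgical periods apart for efficacy data.

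**The concern.** Long-term safety is the primary objective. The rule takes a defined stretch of follow-up out of the numerator of nearly every AE table, while the subjects concerned stay in the denominator.

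By the SAP's own definitions the removed events are treatment-emergent. SAP 8.2.2 counts any AE on or after Study Day 1, apart from events carried over without worsening. SAP 5.3.4 runs the safety period from Study Day 1 to the last recorded date with no surgical break. The SAP gives no reason for the exclusion.

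The weeks after major surgery matter for safety. Protocol 15.2.3 requires a vascular thrombotic event associated with the study drug to be reported as a serious adverse event (SAE). One that starts the day after surgery would be absent from the preferred-term, severe-event, relationship and SAE tables. The surgery itself, if reported as an SAE, could appear in the SAE table.

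**Working it through.** **1. Which onset days are removed.** Call the day of surgery day 0. Under SAP 5.3.3 the pre-surgical dose falls on day 0 or the day before, so the period starts on day 0 or day -1.

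- Start on day -1: days -1 and 0 are kept; day 1 to the end of the period is removed.
- Start on day 0: day 0 is kept; day 1 to the end of the period is removed.

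Either way, the removed events are those that start after the day of surgery and before the period ends. An event dated only to a month or year is removed only if its whole possible onset range lies inside the period. An event with no onset date at all is kept (SAP 8.2).

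**2. Which tables are affected.** They are system organ class and preferred term (8.2.2), descending incidence and severe events (8.2.3), severity (8.2.4), relationship (8.2.5) and treatment-emergent SAEs (8.2.6). None of these sections makes an exception for surgical periods.

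**3. What remains.** The overview's surgery column counts subjects with any, related, serious and related serious events, discontinuations and deaths. It gives no terms, and its denominator is not stated. The events also appear in the full AE listing and in a separate surgical-period listing. The list of tables contains "Summary of rFVIII Fc treatment-emergent serious adverse events" and five titles headed as surgery-subgroup tables: response, injections and dose, blood loss, consumption and bleeds. None of the five covers AEs.

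**4. What is not affected.** Inhibitor results, which include samples from surgical periods (8.3.2); AEs around minor surgery; and AEs after the period ends.

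**5. Size.** The planned pool reproduces the figure in SAP 3.1: 144 + 50 + 12 + 8 = 214 (SAP 3.3.1). The plan gives no figure for the effect itself. If k subjects have a given term only in the removed window, the shortfall in that term's incidence is 100 × k / 214 points. One subject gives 100 × 1 / 214 = 0.47 points.

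Let S be the number of subjects with major surgery. Since k cannot exceed S, the ceiling is 100 × S / 214. The values of S and the 10% share below are assumptions.

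| S (assumed) | Ceiling, points | Shortfall if 10% of S affected, points |
|---|---|---|
| 5 | 2.34 | 0.23 |
| 10 | 4.67 | 0.47 |
| 20 | 9.35 | 0.93 |
| 30 | 14.02 | 1.40 |

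**6. Example for a rare term.** Assume S = 20 and two subjects with the term, both only in the window. The intervals are exact (Clopper-Pearson) and for illustration only.

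- Shown in the preferred-term table: 0/214 = 0% (95% CI 0 to 1.71%).
- True incidence in the full set: 2/214 = 0.93% (0.11 to 3.34%).
- On the surgery-subgroup denominator: 2/20 = 10% (1.2 to 31.7%).

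Both subjects would still be counted in the overview's surgery column, without the term.

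**The case against.** The strongest defence is that the rule is prespecified and loses no event. All AEs are listed, surgical-period AEs are flagged and listed again, and SAEs, discontinuations and deaths have their own listings. SAP 7.6 calls the surgery subgroup small and relies mainly on listings for its efficacy data. Keeping post-operative events out of a long-term drug-safety profile is a legitimate aim, and one added table would serve it without deleting the rule. This stands in part: the fault is in how events are tabulated, not in their collection. But listings and a column without terms do not give incidence by preferred term, and a zero in the main table for an event that occurred is misleading however small the subgroup.

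Other points against:

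- **The table list is only indicative.** Its titles are described as suggested, and it also omits tables that the SAP text orders, such as those for severity and severe events. SAP 8.2 also refers to summaries of surgical-period AEs. So absence from the list is weak evidence by itself. The explicit exclusion in 8.2.1 carries the point.
- **The full Safety Analysis Set is the right denominator.** This is correct. The defect is the cut in the numerator, and the fix leaves the denominator alone.
- **The protocol is silent on surgical-period AEs.** True, so there is no direct contradiction. But it plans AE incidence without an exclusion and separates surgical periods for efficacy data.
- **The magnitudes are assumed.** They are. The ceiling would require every surgery subject to have the same term, and only in the window, so the 10% column is the more realistic guide. Also, 214 is the planned pool, not the Safety Analysis Set that will be observed.

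**Conclusion.** The concern holds and should be fixed. As written, SAP 8.2.1 leaves AEs that start after the day of major surgery and before the period ends out of every table that gives terms, severity, relationship or seriousness by term. Incidence in those tables is at or below the incidence defined in SAP 8.2 and planned in Protocol 16.6.2, never above it.

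The actual size is unknown, because it depends on the number of major surgeries and the post-operative event rate. Each affected subject costs 0.47 points of incidence for a term if 214 subjects are analysed. The assumed cases with 10% of 5 to 30 surgery subjects affected give 0.23 to 1.40 points. The practical harm is greatest for rare terms, which can vanish. The primary endpoint, inhibitor development, is not touched.

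**What to change.** 1. Delete the exclusion sentence in SAP 8.2.1, so that all treatment-emergent AEs and SAEs enter the system organ class/preferred term, descending-incidence, severe, severity, relationship and SAE tables.
2. Add one system organ class/preferred term table restricted to major surgical/rehabilitation periods, with the surgery subgroup as its stated denominator, and put it in the table list.
3. Show the SAE table with and without the major-surgery entries, because the rule for reporting them changed at Amendment 2.
4. Reconcile SAP 8 with 8.2.1 on whether the overview has a surgery column, and state that column's denominator.

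The cost is SAP wording, a re-run of the AE tables and a few added outputs, with no new data. The downside is that AE rates will look slightly less favourable and events caused by the procedure will enter the main tables. The restricted table lets readers separate them.

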8.2.2. Treatment-emergent Adverse Events

In general, an AE will be regarded as treatment-emergent if it was present prior to receiving the first injection of rFVIIIIFc in the parent study and subsequently worsened in severity, or was not present prior to receiving the first injection but subsequently appeared before the subject's last visit on study or the follow-up phone call, whichever came later (or the date of withdrawal/loss to follow-up).

All AEs that occurred on or after the 8HA01EXT Study Day 1 will be considered treatment-emergent in study 8HA01EXT, regardless of the gap between the parent study and study 8HA01EXT. AEs that were treatment-emergent in the parent studies and carried over to study 8HA01EXT without worsening in severity will be considered the same AEs and will not be counted again in study 8HA01EXT.

The incidence of TEAEs will be summarized by system organ class (SOC) and preferred term. Unless specified otherwise, SOCs and preferred terms within each SOC will be presented alphabetically. For the purpose of summarization, a subject is counted once in a SOC or preferred term if the subject reported one or more events in that SOC or preferred term. Unless specified otherwise, percentages will be based on the number of subjects in the Safety Analysis Set.

8.2.3. Adverse Events in Descending Order of Incidence

A table will be provided which displays TEAE preferred terms in descending order of incidence. Only preferred terms will be included in this table (i.e., the display will not include SOCs).

A similar table will be provided for severe TEAEs. AEs for which the assessment of severity is missing will be included in this table.

8.2.4. Severity of Adverse Events

AEs are classified by the Investigator for severity ("Mild", "Moderate", and "Severe"). A summary of TEAEs by system organ class, preferred term, and severity will be presented. AEs with a missing severity will be counted as "Severe" in the summary table. A subject will be counted once for each SOC and preferred term based on the greatest severity within that SOC and preferred term, respectively.

8.2.5. Relationship of Adverse Events to Study Drug

AEs are classified by the Investigator for relationship to study drug ("Not related" and "Related"). A summary of TEAEs by SOC, preferred term, and relationship will be presented. AEs with a missing relationship will be counted as "Related" in the summary table. A subject will be counted once for each SOC and preferred term based on the highest relationship within that SOC and preferred term, respectively.

8.2.6. Serious Adverse Events

Any AE reported as resulting in death, immediate risk of death (life threatening), inpatient hospitalization or prolongation of existing hospitalization, persistent or significant disability/incapacity, or a congenital/anomaly/birth defect will be classified as an SAE by the Investigator. An SAE may also be any other medically important event that, in the opinion of

the Investigator, may jeopardize the subject or may require intervention to prevent one of the other outcomes listed above.

All SAEs will be listed; treatment-emergent SAEs will be summarized by system organ class and preferred term.

8.2.7. Adverse Events Leading to Treatment Discontinuation or Withdrawal From the Study

AEs leading to treatment discontinuation or withdrawal from the study will be listed. All AEs reported on the AE log for the item “Was the subject terminated from this study due to this AE” with a response of “Yes” or “Action Taken with Study Drug” with a response of “Drug Withdrawn” will be included.

8.2.8. Deaths on Study

A listing of deaths occurring on study 8HA01EXT will be provided.

8.3. Clinical Laboratory Evaluations

Analyses for laboratory data involving baseline value will be based on study 8HA01EXT Baseline (as defined above in Section 5.1).

All summaries will be structured such that the hematology and chemistry tests are presented in the order shown in the tables provided in Section 8.3.1.

All laboratory data will be provided in data listings; abnormal values relative to laboratory normal ranges will be identified. Laboratory evaluations taken during major surgical/rehabilitation periods will be included in the listings and flagged.

8.3.1. Hematology and Chemistry

Hematology measurements that will be collected and listed include white blood cell count (WBC), differential, hemoglobin, hematocrit, and platelet count.

Chemistry measurements that will be collected and listed include electrolytes (sodium, potassium, chloride), glucose, total protein, total bilirubin, alanine aminotransferase (ALT), aspartate aminotransferase (AST), alkaline phosphatase (ALP) [collected for subjects from study 997HA301 only], blood urea nitrogen (BUN), and serum creatinine.

